Subgroup analyses will be conducted for PFS for the stratification factors.

Secondary Analyses

Clinical Benefit:

- Improvement in response

Improvement in response will be assessed by calculating the percentage of subjects who change from PR at baseline to CR during the study. Improvement in response will also be assessed by providing the frequency and percentage of subjects with positive minimal residual disease (MRD). These rates will be compared between treatment groups with the Cochran-Mantel-Haenszel test adjusting for stratification factors (response, number of prior treatments and type of prior treatment).

- Overall survival

Overall survival is defined as time from randomization to date of death. The same analysis will be conducted as described for the primary endpoint, PFS.

- Time to next therapy

Time to next therapy is defined as the time from randomization to date of receiving the next CLL treatment. The same analysis will be conducted as described for the primary endpoint.

- Progression-free survival after next-line therapy

This endpoint will be defined as time from randomization until progression or death following next-line therapy and counting as events deaths prior to next-line therapy. [REDACTED]

- Time to progression after next-line therapy

This endpoint will be defined as time from progression following randomization until progression or death following next-line therapy and counting as events deaths prior to next-line therapy. [REDACTED]

- Frequency of transfusions

The number and percentage of subjects who receive blood transfusions during the study will be provided.

- Evaluation of myelosuppression (anemia, neutropenia, thrombocytopenia)

The number and percentage of patients with myelosuppression will be provided.

- IgG, IgA, IgM

Summaries of IgG, IgA, and IgM will be provided at scheduled visits.

Disease Markers:

- Minimal Residual Disease (MRD)

The number and percentage of subjects with positive MRD will be provided. The proportion of subjects with positive MRD will be compared between treatment groups with the Cochran-Mantel-Haenszel test adjusting for stratification factors (response, number of prior treatments and type of prior treatment).

- B-cell monitoring

CD5/CD19 change from baseline will be summarized to assess the treatment effect. The number and percentage of subjects with complete B-cell depletion will be summarized.

- Prognostic markers correlating with clinical response

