## 11. EFFICACY

All efficacy analyses will be based on the ITT population as defined in Section 6 unless otherwise specified. All analyses will be presented by treatment arm.

Efficacy assessments are based on IWCLL updated NCI-WG CLL criteria (Hallek, 2008) to assess clinical activity and disease status. Primary assessments will be based on

investigator assessment. Independent Reviewer Committee assessments will be considered as supplementary for sensitivity analyses.

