## **11.2. Secondary Efficacy Analyses**

### **Clinical Benefit:**

- Improvement in response

Improvement in response will be assessed by calculating the percentage of subjects who change from PR at baseline to CR during the study. Improvement in response will also be assessed by providing the frequency and percentage of subjects with negative and positive minimal residual disease (MRD). These rates will be compared between treatment groups with the Cochran-Mantel-Haenszel test adjusting for stratification factors (response at entry, number of prior treatments and type of prior treatment). The 95% confidence intervals will also be calculated for rates in each arm.

- Overall survival

Overall survival is defined as time (in months) from the randomization date to the date of death due to any cause. For subjects who do not die, time of death will be censored at the date of last contact. Survival distributions will be estimated using the Kaplan-Meier method, and survival curves will be compared using a stratified log-rank test. The same analysis will be conducted as described for the primary endpoint, PFS.

The analysis of overall survival will be performed when the second interim analysis for PFS takes place as well as at the end of the study. Subjects will be followed for 5 years after the 2 year treatment period.

- Time to next therapy

Time to next therapy is defined as the time (in months) from the randomization date to the date of receiving the next CLL treatment. For subjects who do not receive another CLL therapy, time of next therapy will be censored at the date of last contact. The same analysis will be conducted as described for the primary endpoint, PFS.

The analysis of time to next therapy will be performed when the second interim analysis for PFS takes place as well as at the end of the study.

- Progression-free survival after next-line therapy

This endpoint will be defined as the time (in months) from randomization until progression or death following next-line therapy and counting as events deaths prior to next-line therapy. Analysis of this endpoint will only include subjects who received next-line therapy and subjects who died prior to receiving next-line therapy. Subjects who receive next-line therapy and who do not have progression or death after next-line therapy will be censored at their last date of contact. If a subject dies prior to next-line therapy, this will count as an event. [REDACTED]

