## 1 Introduction

OMB157C2301 (OMB112517) is a Phase III, open-label, randomized, multicenter trial to evaluate efficacy and safety of ofatumumab (OFA) maintenance treatment versus no further treatment in subjects with relapsed chronic lymphocytic leukemia (CLL) who have responded to induction therapy using a parallel design.

**Background:** The primary endpoint has been met at the protocol-defined interim analysis that was triggered after 187 events were observed (data cut-off date on June, 19 2014). OFA maintenance demonstrated a significant improvement in PFS ( $p < 0.0001$ ) as assessed by the investigator over Obs (OFA maintenance: median [mPFS] of 29.4 months, Obs: mPFS of 15.2 months; HR 0.50; 95% CI 0.38, 0.66). A 120 day Safety update has been performed (safety update data cut-off (28-Feb-2015)).

Statistical Analyses Plan (SAP) for the current planned analysis is based on the efficacy and safety data collected up to 20-Feb-2017, the cut-off date when 280 PFS events or death occurred in the study. The analysis results will be used for descriptive purpose only. In particular supportive analysis to the primary endpoint will be provided.

All analyses that were done for the interim CSR (Dated 11-Sep-2014, Document # 2014N213614\_00) will be done for this analysis *except* the following outputs (see [Table 1](#)).

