14.0080	Forest Plot of the Difference of Mean Change from Baseline Score (95% CI) in Patient Reported EORTC QLQ-C30 for Global Health Status and Functional Scales
14.0210	Forest Plot of Difference of Mean Change from Baseline Score (95% Confidence Intervals) in B-symptom for patients reported by Domain and Disease Score (high/Very High Risk)

Besides that, the following outputs will be added (Table 3.0929 , Table 3.1800, Table 3.0421) on Table of content (TOC) for this analysis based on 280 PFS events (see [Appendix 1](#)).

- Summary of SAEs before or after start of next anticancer therapy (Table 3.0929)
- Time since last treatment with Ofatumumab for patients who have not started next anticancer therapy (Table 3.1800)
- Summary of Fatal SAE (Table 3.0421)

All the data rules will follow the interim CSR ones. The TOC for the analysis based on 280 PFS events is documented in a separate document, attached for reference in Appendix 1.

## 2 Appendix 1

Table of content for planned analysis based on 280 PFS events

TABLES	
Table No.	Title
Study Population	

1.0010	Summary of Study Populations
1.1010	Summary of Number of Subjects By Centre
1.1110	Summary of Subject Disposition
1.1112	Summary of Subject Disposition at each Study Phase
1.1120	Summary of Study Treatment Status
1.1210	Summary of Inclusion/Exclusion Criteria Deviations
1.1310	Summary of Protocol Deviations
1.2010	Summary of Demographic Characteristics
1.2011	Summary of Demographic Characteristics By Age
1.2020	Summary of Race and Racial Combinations
1.2030	Summary of Race and Racial Combinations Details
1.2032	Summary of Actual Stratification Factors
1.3010	Summary of Covariates for Time-To-Event Endpoint
1.4010	Summary of Past Medical Conditions
1.4020	Summary of Current Medical Conditions
1.4110	Summary of Disease Characteristics at Initial Diagnosis
1.4120	Summary of Disease Characteristics at Screening
1.4130	Summary of Baseline Hematology Values
1.4140	Summary of IgA, IgG, and IgM at Baseline
1.4142	Summary of Prognostic Markers at Baseline
1.4144	Summary of B-Symptoms at Baseline
1.4150	Summary of Prior Anti-Cancer Therapy
1.4160	Summary of Type of Prior Anti-Cancer Therapy
1.4170	Summary of Number of Prior Anti-Cancer Therapy Regimens
1.4180	Summary of Best Response to Most Recent Prior Anti-Cancer Therapy
1.4182	Summary of Most Recent Types of Prior Chemoimmunotherapy
1.4184	Summary of Best Response to Most Recent Type of Prior Chemoimmunotherapy

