## 1 Introduction

OMB157C2301 (OMB112517) is a Phase III, open-label, randomized, multicenter trial to evaluate efficacy and safety of ofatumumab (OFA) maintenance treatment versus no further treatment in subjects with relapsed chronic lymphocytic leukemia (CLL) who have responded to induction therapy using a parallel design.

**Background:** The primary endpoint has been met at the protocol-defined interim analysis that was triggered after 187 events were observed (data cut-off date on June, 19 2014). OFA maintenance demonstrated a significant improvement in PFS ( $p < 0.0001$ ) as assessed by the investigator over Obs (OFA maintenance: median [mPFS] of 29.4 months, Obs: mPFS of 15.2 months; HR 0.50; 95% CI 0.38, 0.66). A 120 day Safety update has been performed (safety update data cut-off (28-Feb-2015)).

Then, a planned analysis has been performed based on efficacy and safety data collected up to 20-Feb-2017, the cut-off date when 280 PFS events or death occurred in the study. The analysis of PFS based on investigator-assessment showed an estimated 45% risk reduction in the OFA maintenance arm compared to the Obs arm (Hazard ratio: 0.55 with 95% CI: 0.43,0.70). The median PFS times (95% CI) are 34.17 months (29.70, 38.01) and 16.89 months (12.98, 20.37) respectively for OFA maintenance arm and Obs arm.

**Analysis Plan:** The current version of the statistical analysis plan (SAP) for the final analysis is based on data collected up to last patient last visit. All the analysis conventions will follow the previous SAP (published on 02-Jun-2017 and addendum on 11-Jan-2018). Final analysis of PFS was performed at protocol defined 280 events and will not be updated. The analysis results will be used for descriptive purpose only.

The population pharmacokinetic analyses [redacted] using the established PopPK model [GlaxoSmithKline Document Number [2012N156806\\_002](#)] will not be repeated, as the PopPK model takes into account data from Cycle 1 Week1, Cycle 1 week 9 and Cycle 4. The majority of this data was already available at the time of the data cut-off 19-Jun-2014 and described in the PopPK report [GlaxoSmithKline Document Number [2014N215557\\_00](#)] in the interim CSR.

In case psychometric validation of B-symptoms score and QLQ-CLL16 domain scores will be performed, this would be documented in separate document and will not be part of the final analysis CSR.

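### PFS after next-line therapy runs from randomization but leaves out subjects alive and not re-treated, so a benefit that comes through delayed re-treatment is understated (minor; descriptive endpoint)

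*SAP*

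**What the plan says.** - **Analysis set.** SAP Section 11.2 starts the clock at randomization and counts progression or death after next-line therapy, plus deaths before it. It then states: "Analysis of this endpoint will only include subjects who received next-line therapy and subjects who died prior to receiving next-line therapy". Its censoring rule covers only re-treated subjects without a later event. Subjects alive and not re-treated are neither events nor censored.
- **Same section, different handling.** For time to next therapy: "For subjects who do not receive another CLL therapy, time of next therapy will be censored at the date of last contact".
- **Protocol.** Section 8.3.5.1 defines the endpoint as "time from randomization until progression or death following next-line therapy", with earlier deaths as events. No restriction is visible, but text straight after the definition is redacted. Protocol Section 8.3.1.1 makes ITT the primary population for efficacy.
- **Default population.** SAP Section 11: "All efficacy analyses will be based on the ITT population as defined in Section 6 unless otherwise specified". An exception is allowed; the visible text gives no reason for this one.
- **Later analyses.** The SAP for the 280-event analysis says "All the data rules will follow the interim CSR ones"; the SAP for the final analysis says "All the analysis conventions will follow the previous SAP". Both list Table 2.1140 and Figure 12.0070 for this endpoint.
- **Status.** SAP Sections 7 and 8.4 put only time to next therapy and OS in the inferential sequence after PFS. Both later SAPs call their results descriptive.

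**The concern.** With a clock that starts at randomization, a subject alive and not re-treated has contributed valid event-free time. Censoring keeps that time; deletion discards it. Membership of the analysed set is also decided after randomization, by an outcome that treatment affects. If maintenance delays progression and hence re-treatment, the deleted subjects are disproportionately ofatumumab subjects who are doing well. Those who remain in that arm are the ones re-treated early or dead. The by-arm Kaplan-Meier curves and medians are then pulled together. What is at stake is the reported description of a protocol-listed secondary endpoint, namely whether the maintenance benefit lasts through the next line of treatment.

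**Working it through.** **No plan figure to reproduce.** The documents give no effect size, event count or power for this endpoint, and no times to re-treatment. The 280-event target concerns PFS only.

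**Inputs from the documents.** PFS medians 16.89 (observation) and 34.17 months (ofatumumab), from the final-analysis SAP introduction. Accrual 12 per month, so 480/12 = 40 months. Cut-offs 19 June 2014 (187 events) and 20 February 2017 ("based on the efficacy and safety data collected up to 20-Feb-2017, the cut-off date when 280 PFS events or death occurred in the study"): 977 days / 30.4375 = 32.1 months apart. Planned follow-up 2 + 5 years = 84 months.

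**Assumed.** Exponential times; mean 6 months from progression to next therapy; next-line PFS median 24 months in both arms; deaths before next therapy 0 to 0.4% per month; 240 subjects per arm. The two medians imply a PFS hazard ratio of 16.89/34.17 = 0.49, somewhat stronger than the reported 0.55.

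**Step 1: who is deleted, by hand.** Let a = ln 2 / median PFS, b = 1/6, and δ = monthly death rate. The chance of being alive and not re-treated after F months is

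P = e^(-δF) × [b·e^(-aF) - a·e^(-bF)] / (b - a).

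At F = 84 with δ = 0, the term in e^(-bF) is negligible:
- Observation: a = 0.0410, P = 0.1667 × 0.0318 / 0.1256 = 4.2%.
- Ofatumumab: a = 0.0203, P = 0.1667 × 0.1820 / 0.1464 = 20.7%.

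With δ = 0.004, multiply by e^(-0.336) = 0.715, giving 3.0% and 14.8%. Even at full follow-up the deletion is about five to one.

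**Step 2: effect on the hazard ratio, by simulation.** Each simulated trial was analysed twice by Cox model: all randomized with un-retreated survivors censored, then the SAP subset. Ranges run over the death rates.

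| Cut-off | All randomized | SAP subset |
|---|---|---|
| 280-event date, drop-out about 1.5-1.9% per month to give about 280 PFS events | 0.57-0.72 | 0.82-1.02 |
| 84 months per subject, no drop-out | 0.60-0.71 | 0.78-0.88 |

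In the first row about 60% of observation and 41-46% of ofatumumab subjects are retained. Of 240 per arm, that deletes about 0.40 × 240 = 96 against 0.54 × 240 = 130 to 0.59 × 240 = 142. Drop-out is needed for a realistic count: without it the model has about 360-373 PFS events by that date. The hazard ratios barely depend on it (0.58-0.71 to 0.85-0.99 without drop-out).

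**Step 3: when the bias is absent.** With no treatment effect the result is 1.00 under both rules. With equal PFS and next-line medians of 24 vs 48 months, the 84-month hazard ratio is 0.55-0.59 for all randomized and 0.54-0.58 for the subset.

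**Step 4: sensitivity.** With a gap of 3-12 months and next-line median of 12-36 months, without drop-out, the 280-event date gives 0.54-0.79 against 0.80-1.10, and 84 months gives 0.54-0.76 against 0.72-0.94. A separate model specified time to next therapy directly (28 vs 39.2 or 28 vs 56 months). Over 36 delay-only combinations it gave 0.61-0.93 for all randomized and 0.78-1.26 for the subset, with the subset value higher every time.

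**The case against.** **The consequence is limited.** The endpoint is non-inferential, later results are descriptive, the error runs against the sponsor's drug, and un-retreated subjects remain visible in time to next therapy. All of this stands, and it is why the point is minor.

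**A SAP may fill in what the protocol leaves open.** A reader might infer that the SAP contradicts the protocol. The documents do not support that: the protocol text is redacted after the definition and its visible part is silent on subjects alive and not re-treated. The firmer comparisons are with the SAP's own rule for time to next therapy and with ITT as primary population.

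**The endpoint is about what follows next-line therapy, so conditioning on it is natural.** That would hold if the clock started at next-line therapy. It starts at randomization.

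**Carry-forward is not proven.** The 280-event SAP points to the interim study report, which is not supplied. The final SAP also cites an addendum that cannot be identified in these documents. SAP Section 8 allows deviations to be recorded in the study report. That the rule governs the later tables is a reasonable inference only.

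**An ITT-titled variant exists.** Table 2.5010 was among the interim outputs ("All analyses that were done for the interim CSR" introduces the list of exclusions that names it). It changes the event definition, its censoring rules are not visible, and it is absent from both later output lists.

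**The interim looks worst.** A reader might take modelled subset hazard ratios above 1 at 187 events as a likely apparent reversal. That reading is too strong: in the model only about 1-7 subset subjects per arm are still at risk at 36 months.

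**Conclusion.** The concern holds, at minor severity. The restriction is complete, unredacted text, and it selects on an outcome that treatment affects. The direction needs only that maintenance delays re-treatment. The size rests on assumed re-treatment, next-line and death rates: a true hazard ratio of roughly 0.6-0.7 could be reported as roughly 0.8-1.0 at the 280-event cut-off, and about 0.8-0.9 at 84 months. The bias shrinks with follow-up but does not vanish.

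Two wider readings are not supported. A reader might infer that the trial's efficacy claims are affected; PFS, time to next therapy and OS do not use this rule. A reader might also extend the point to time to progression after next-line therapy, which has a similar inclusion sentence. That clock starts at progression, so it is conditional on progression by construction, and the same model shows no shift between arms (about 1.00 under either rule).

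**What to change.** In SAP Section 11.2, replace the restricting sentence for PFS after next-line therapy with: *All randomized subjects are included. Subjects alive without next-line therapy are censored at the date of last contact.* Rerun Table 2.1140 and Figure 12.0070, and state in the report which rule produced each version. Keep the subset, if wanted, only as a labelled supplementary description. Do not substitute Table 2.5010, because it changes the event definition. Leave time to progression after next-line therapy as it is unless a separate case is made. The cost is a one-sentence replacement and two reruns, with no new data.

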2. OBJECTIVES

Primary objective:

[figure not shown]
- To evaluate PFS of subjects treated with ofatumumab maintenance treatment compared to no further treatment after remission induction in subjects with relapsed chronic CLL

Secondary objectives:

- To evaluate the improvement in response, improvement in response time to next CLL treatment and overall survival in subjects receiving ofatumumab maintenance compared to no further treatment
- To evaluate the PFS after next-line therapy and the time to progression after next-line therapy
- To evaluate the safety and tolerability in subjects with CLL receiving ofatumumab maintenance compared to no further treatment
- To evaluate the health-related quality of life in subjects with CLL receiving ofatumumab maintenance compared to no further treatment as assessed by changes in patient reported outcome (PRO) measures relative to baseline
- To evaluate prognostic marker correlation with clinical response in subjects with CLL receiving ofatumumab maintenance compared to no further treatment
- To evaluate ofatumumab pharmacokinetic parameters in subjects with CLL receiving maintenance ofatumumab every 2 months

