3.1.4. Follow-up Phase

Survival and disease status assessments (physical examination and evaluation of peripheral blood samples) will be performed post treatment every 3 months for 5 years after last treatment.

A bone marrow examination is required to confirm Complete Remission (CR) at least 2 months after completion of therapy and when a subject fulfills the International Workshop for Chronic Lymphocytic Leukemia (IWCLL) updated National Cancer Institute-Sponsored Working Group (NCI-WG) requirements for Complete Remission (CR) [Hallek, 2008]. Previous results may be used or if not available, a bone marrow exam may be done at screening. If a subject's response improves to a CR while on study, then a bone marrow examination is required to confirm CR at least 2 months after response as per the updated IWCLL NCI-WG requirements for CR [Hallek, 2008].

Additionally, CT Scans are required yearly while on study, including during follow-up, and at disease progression, whenever that may occur.

Subjects demonstrating disease progression will be followed for survival status until study completion. Follow-up assessment after disease progression on treatment will assess survival status, date of next CLL therapy, type of therapy and response to therapy. It is acceptable for the information for survival follow-up visits to be collected remotely (via telephone, email), as necessary. The frequency of the survival follow-up visits should be per local standard of care, suggested every 3 months for CLL. Minimally, this should be collected at least annually.

PRO measures (EORTC QLQ-C30, EORTC QLQ-CLL16, EQ-5D and a Health Change Questionnaire) will be administered for completion by the subject at follow-up visits, as per Section 6.5.6.

Please refer to Section 6: Study Assessments and Procedures for detailed assessment instructions.

Supplementary study conduct information not mandated to be present in this protocol is provided in the accompanying Study Procedures Manual (SPM). The SPM will provide the site personnel with additional administrative and detailed technical information.

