- Time to progression after next-line therapy

This endpoint will be defined as time (in months) from progression following randomization until progression or death following next-line therapy and counting as events deaths prior to next-line therapy. Analysis of this endpoint will only include subjects who received next-line therapy and who also had PD prior to receiving next-line therapy. Subjects with PD who died prior to receiving next-line therapy will also be included. Subjects who receive next-line therapy with a PD prior to receiving next line therapy and who do not have progression or death after next-line therapy will be censored at their last date of contact. If a subject dies prior to next-line therapy, this will count as an event. [REDACTED]

- Changes in patient reported outcome scores

Area under the curve (AUC) of change from baseline over time in the EORTC QLQ-C30, EORTC QLQ-CLL16 domain scores and total scores as well as the EQ-5D utility and VAS scores will be evaluated. Details of the methods used to evaluate changes in PRO domain and total scores will be provided in the Health Outcomes section of the RAP.

- Improvement of ECOG performance status

Improvement is defined as a decrease from baseline by at least one step on the ECOG performance status scale (improvement categorized as yes or no). The proportion of subjects with improvement will be compared between treatment groups with the Cochran-Mantel-Haenszel test adjusting for stratification factors (response at entry, number of prior treatments and type of prior treatment).

- B-symptoms/Constitutional symptoms

The proportion of subjects with no night sweats, no weight loss, no fever and no extreme fatigue will be summarized and compared to the proportion of subjects with at least one of the following: night sweats, weight loss, fever or extreme fatigue. The proportions will be compared between treatment groups with the Cochran-Mantel-Haenszel test adjusting for stratification factors (response at entry, number of prior treatments and type of prior treatment).

- Incidences of and number of subjects with grade 3 and 4 infections

The number and percentage of subjects with grade 3, 4 and 5 infections will be summarized by treatment group.

- Evaluation of myelosuppression (anemia, neutropenia, thrombocytopenia)

The number and percentage of subjects with myelosuppression will be summarized by treatment group.

- Frequency of transfusions

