2.2058	Summary of CD5-CD19+ Change from Baseline over time Excluding data After Taking Anti-Cancer Therapy
2.2059	Summary of CD5-CD19+ Percent Change from Baseline over time Excluding data After Taking Anti-Cancer Therapy
2.2060	Summary of Subjects with Complete B-cell Depletion
2.2064	Summary of Subjects with near-Complete B-cell Depletion
2.2070	Summary of Subjects with Positive and Negative Minimal Residual Disease (MRD) at each timepoint

2.2075	Summary of Subjects with Positive and Negative Minimal Residual Disease (MRD) at each Timepoint by Response at Entry
2.2080	Summary of Cox Proportional Hazards Regression Model For Relationship Between Investigator Assessed Progression-Free Survival and prognostic markers
2.4412	Summary of Kaplan-Meier Estimates of Overall Survival by IgVH Mutational Status 1 (collected)
2.4413	Summary of Kaplan-Meier Estimates of Overall Survival by IgVH Mutational Status 2 (97% cut-off)
2.4414	Summary of Cox Proportional Hazards Regression Models for Relationship between Overall Survival and Prognostic Markers (Univariate Models)
2.4415	Summary of Cox Proportional Hazards Regression Models for Relationship between Overall Survival Including IgVH Mutational Status 1 as One of the Covariates (Multivariate Model)
2.5010	Summary of KM Estimates of Investigator-assessed Progression-Free Survival After Next-Line Therapy Where Events of PD from the NTX eCRF (best response) Are also included and Taking Censored Death as an Event, for the ITT Population
2.5020	Summary of Best Response to First Next-Line Therapy
2.8000	Summary of Kaplan-Meier Estimates of Investigator-Assessed Progression-Free Survival by Disease Score 2 – High/Very High Risk
2.8005	Summary of Kaplan-Meier Estimates of Overall Survival by Disease Score 2 – High/Very High Risk
2.8020	Summary of Severity Scale Based on Selected Factors by Disease Score 2 – High/Very High Risk
2.8060	Summary of Kaplan-Meier Estimates of Time to Next Therapy Treating Death as an Event by Disease Score 2 – High/Very High Risk
2.8090	Summary of Kaplan-Meier Estimates of Sensitivity Analysis of Investigator-Assessed Progression-Free Survival Where Events Based on CT-scan are Included by Disease Score 2 – High/Very High Risk
2.8100	Summary of Kaplan-Meier Estimates of IRC-Assessed Progression-Free Survival by Disease Score 2– High/Very High Risk

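### PFS and time to progression after next-line therapy censor at last contact, although progression after the next line is not systematically recorded, so unrecorded progressions count as progression-free time

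*SAP*

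**What the plan says.** **Objective.** Protocol section 2 includes, among the secondary objectives, "To evaluate the PFS after next-line therapy and the time to progression after next-line therapy". Progression after the next line is an event in both endpoints (protocol 8.3.5.1, SAP 11.2).

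**Follow-up after first progression.** Protocol 3.1.4 states: "Subjects demonstrating disease progression will be followed for survival status until study completion". The items are then listed: "Follow-up assessment after disease progression on treatment will assess survival status, date of next CLL therapy, type of therapy and response to therapy". SAP section 3 (Follow-up Phase) repeats this list. On the mode of contact, the protocol says: "It is acceptable for the information for survival follow-up visits to be collected remotely (via telephone, email), as necessary". Frequency follows local practice, with every 3 months suggested, and: "Minimally, this should be collected at least annually".

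**Censoring.** For PFS after next-line therapy, treated subjects who "do not have progression or death after next-line therapy will be censored at their last date of contact". For time to progression after next-line therapy, subjects with no "progression or death after next-line therapy will be censored at their last date of contact".

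**Contrast with primary PFS.** SAP 11.1 and its Table 1 censor primary PFS at the last adequate disease assessment. SAP 9.2.12 also censors there when progression or death follows a long gap (140 days on study, 210 days in follow-up), because the event time is then uncertain.

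**Outputs.** Output 2.5010 is a version of PFS after next-line therapy "Where Events of PD from the NTX eCRF (best response) Are also included". It is on the list of outputs not produced at 280 events and is absent from the final-analysis list. Both later analyses keep 2.1140 and 2.1150, the main tables for the two endpoints.

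**The concern.** The data collected and the censoring rule do not fit together. For overall survival, censoring at last contact is right, because the contact itself establishes that the subject is alive. For an endpoint that includes progression, the same date is valid only if progression would have been detected and recorded by then. After first progression the protocol does not secure that.

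Consider a subject who starts next-line therapy at month 16, progresses on it at month 24 without that being recorded, and is reached alive by telephone at month 60. The rule censors this subject at month 60, adding 36 months of progression-free time that did not exist.

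These endpoints are meant to show whether maintenance preserves or erodes the benefit of the next line. The fewer second progressions are recorded, the closer they drift towards overall survival, and the less they can answer that question.

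**Working it through.** The plan states no sample size, event count or power for either next-line endpoint, so there is no figure to reproduce. The 280-event calculation concerns primary PFS only and is not in question.

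**Inputs for the illustration**
- First-PFS median 15.2 months: the observation-arm interim result in the Introduction to the SAP for the 280-event analysis.
- Assumed: next-line therapy starts at first progression; median 12 months from there to second progression; median 48 months from there to death; last contact uniform 12 to 60 months after next-line start; all other times exponential and independent.
- Assumed share of second progressions recorded, q: 100, 75, 50 and 25%. The documents give no value.

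**Model.** Let T1 be time to first progression, P time from there to second progression, D time from there to death, and U time from there to last contact.
- Second progression recorded: event at T1 + min(P, D).
- Not recorded: event at T1 + D.
- No event by T1 + U: censored at T1 + U.

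**Check from next-line start.** With full recording the hazards add, so the median is 1 / (1/12 + 1/48) = 9.6 months. Simulation also gives 9.6. With 75, 50 and 25% recorded it gives about 13, 20 and 32 months. Under these assumptions this is the scale of time to progression after next-line therapy.

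**PFS after next-line therapy, from randomization** (simulated Kaplan-Meier median)

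| Recorded | Median, months | Overstatement |
|---|---|---|
| 100% | about 30 | – |
| 75% | about 36 | 6 |
| 50% | about 45 | 15 |
| 25% | about 58 | 28 |

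**Wider range.** A second set of runs used a second-progression median of 12 to 28 months, a survival median after first progression of 24 to 60 months, and an administrative cut-off uniform 36 to 85 months from randomization. The observation-arm median was overstated by 1.9 to 4.5 months at 80% recorded, 5.2 to 15.2 at 50%, and 9.1 to 34.6 at 20%. In the ofatumumab arm (first-PFS median 29.4 months) the overstatement at 50% was 5.8 to 16.5 months. With equal recording, both arms are inflated.

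**Effect on the comparison, from next-line start.** With a true second-progression hazard ratio of 0.70, the hazard ratio for progression or death is about 0.75 with full recording. It moves to about 0.84, 0.91 and 0.94 at 75, 50 and 25% recorded. If there is no true difference but one arm has 75% recorded and the other 50%, a spurious hazard ratio of about 0.70 appears in favour of the arm with fewer progressions recorded.

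**The case against.** **Assessments do not stop.** A reader might infer that disease assessment ends at first progression. No sentence says so. Protocol 3.1.4 opens with 3-monthly disease status assessments and requires yearly CT during follow-up. Section 4.4 says that subjects withdrawn from investigational product, progression included, are evaluated for disease status and survival. But 4.4 refers back to 3.1.4, whose paragraph on progressed subjects gives survival follow-up and the short list above. The two sections are unreconciled, and assessment after progression is unscheduled rather than excluded.

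**Some progression is captured.** This stands. Response to next therapy is collected, 2.1140 and 2.1150 are titled as investigator assessed, and the title of 2.5010 says the form's PD is also included, which points to another source in the main table. Recording is incomplete rather than nil. It would therefore be wrong to say that the only analysis using recorded progression was dropped. Output 2.5010 also changes the handling of censored deaths and is specified for the ITT population. Because it is listed as an exception to the interim outputs, it belonged to the interim set.

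**Collection or rules may be specified elsewhere.** The eCRF, the procedures manual and the dataset specifications are not in the documents, and text after both endpoint definitions is redacted. A progression date may be collected. The censoring rule, however, is fully visible and depends on contact, not on disease status.

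**Low stakes.** Both endpoints lie outside the testing sequence (protocol 8.3.3.2, SAP 7), and the SAPs for the 280-event and final analyses call their results descriptive. This limits the importance of the point but does not make the rule correct.

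**Conclusion.** The point holds in this form: recording of progression after next-line therapy is incomplete and unscheduled by the protocol's own list, and censoring at last contact turns each unrecorded progression into progression-free time. The SAP applies a stricter rule to primary PFS, where assessment is better.

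The direction is clear: the medians of both endpoints are too long, and with equal recording a true difference after re-treatment is diluted. The size is not known. The roughly 6, 15 and 28 months at 75, 50 and 25% recorded rest on the assumed times and recording rates; at 80% recorded the wider runs give 1.9 to 4.5 months in the observation arm.

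A reader might also infer a bias in favour of ofatumumab. That would require unequal recording between arms, and the documents give no evidence of it. Primary PFS, time to next therapy and overall survival are not affected.

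**What to change.** 1. In SAP 11.2, for both next-line endpoints, censor subjects with no event at the last date on which disease status after next-line therapy was documented, not at last contact.
2. Count PD reported on the next-therapy eCRF as an event in 2.1140 and 2.1150. The item visible in the documents is a best response, so the SAP must say how such a PD is dated. At the least, keep 2.5010 at the 280-event and final analyses.
3. Add a sensitivity analysis that also counts the start of a further CLL therapy as an event. This changes the endpoint, so it should not replace the main analysis.
4. Reconcile protocol 3.1.4 with 4.4 and, where contacts are still ongoing, record the date of progression after next-line therapy.

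**Cost.** Items 1 to 3 need SAP wording and re-derivation from the therapy and response data collected. Item 4 needs one date field, which helps only while contacts continue; the final analysis uses data up to the last patient's last visit.

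**Downside.** Follow-up for these endpoints becomes shorter and the medians less favourable. Earlier censoring does not recover unobserved progressions, and it could bias the curves downward if status is documented mainly at failure. The report should state this residual bias.
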